Statistical Analysis Plan	
SPSS statistical software package version 22.0 or R software for statistical computing version 3.2.0 will be used.
 
Primary endpoint: change of thickness of expiratory abdominal muscles during MV. Change in thickness will be presented as ratio change compared to baseline, to account for inter-subject variation in baseline thickness. The Wilcoxon signed-rank test will be used to compare changes in baseline and nadir values.
 
Association of categorical independent variables (such as sex, use of corticosteroids during ICU stay, sepsis on admission, etc.) with nadir change in expiratory muscle thickness will be assessed using a Mann-Whitney U test. Association of continuous independent variables (such as duration of mechanical ventilation, days taken to wean, inflammation at inclusion, etc.) with nadir change in expiratory muscle thickness will be assessed using a linear regression model, with change in expiratory muscle thickness as dependent variable. Correlation between change in thickness during the acute stage of MV (5 days) with the total time spent on the ventilator will be examined using a linear regression model.
 
Correlation between diaphragm and expiratory muscles
 
Correlation between change in expiratory muscle thickness and change in diaphragm thickness will be assessed with Pearson's correlation test to compare population means. The difference between change in

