	
expiratory muscle thickness and change in diaphragm thickness will be assessed with a Student's t-test that is paired per subject. This will be done by using the change in thickness between baseline and the last data point obtained. Second, this will be evaluated by using the slope of the thickness curves assessed with a goodness of fit model. We will use a goodness of fit model to first describe the course of both diaphragm and expiratory muscle thickness for each subject. The type of model will be determined after data is obtained.
 
Subgroup analysis
 
Based on the outcomes of these analyses, a subgroup analysis may be performed to compare the subjects with high change in expiratory muscle thickness, to a group with low change in expiratory muscle thickness. A cutoff value to divide these groups will be determined based on how data will emerge. Variables as respiratory function measurements can be compared between groups with a Student's t-test, using group average values. Further, a Kaplan-Meier survival analysis will be carried out to quantify differences in time to wean between groups.

Referenties
	

- and endotracheal tube pressure with bilateral anterolateral magnetic phrenic nerve stimulation in patients in the intensive care unit. *Crit Care Med* 2001; 29:1325-31.

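### The high/low thickness-change cutoff may be set after outcomes are seen, with no exploratory label, and this optional split is the only analysis that names respiratory function

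*Combined protocol and SAP*

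**What the plan says.** The Subgroup analysis paragraph comes last in the SAP and depends on what precedes it: "Based on the outcomes of these analyses, a subgroup analysis may be performed". It divides patients by high or low change in expiratory muscle thickness, and on where to divide it says only "A cutoff value to divide these groups will be determined based on how data will emerge". Two uses follow. First, "Variables as respiratory function measurements can be compared between groups", by Student's t-test. Second, "a Kaplan-Meier survival analysis will be carried out to quantify differences in time to wean between groups"; no test is named for this.

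The preceding analyses already relate thickness change to outcomes. Continuous variables, "such as duration of mechanical ventilation, days taken to wean, inflammation at inclusion, etc", are examined for association "with nadir change in expiratory muscle thickness will be assessed using a linear regression model, with change in expiratory muscle thickness as dependent variable". A further regression covers "Correlation between change in thickness during the acute stage of MV (5 days) with the total time spent on the ventilator". The comparison with the diaphragm uses a third definition of change: "This will be done by using the change in thickness between baseline and the last data point obtained".

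Under Objective, the first secondary objective is the effect of thickness change on expiratory muscle function. Study parameters lists maximum expiratory pressure (MEP) and cough peak flow (CPF) among the function measures. It limits at least some of those measures to selected patients, without giving a number.

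**The concern.** There are two linked problems.

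- **The cutoff is open.** It may be chosen after the relation between thickness change and weaning has been seen, and time to wean is then compared across it. If the choice is influenced by that relation, a reported group difference partly reflects the choice. The same carries over to muscle function to the extent that function and weaning are correlated. The plan also does not say whether nadir, 5-day or last-point change defines a high change, which adds a second free choice.
- **The function objective has no other named analysis.** The only analysis that mentions respiratory function is optional and dichotomised. Splitting a continuous measure discards information, and some function measures may exist for well under 100 patients, so there is little power to spare.

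**Working it through.** **The plan's own figures.** There are none to reproduce on this point. The sample size of 100 comes with no alpha, power, effect size or SD. Everything below therefore assumes two-sided 5%, normal data and the stated correlations. The number of patients with MEP or CPF data is also assumed.

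**1. False-positive rate of the t-test when the cutoff is chosen.** Order the n patients by thickness change, with no true association with outcome. For a cut after the k-th patient,

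t(k) = (m₁ − m₂) / √[ SSE/(n − 2) × (1/k + 1/(n − k)) ],

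where m₁ and m₂ are the group means. A false positive is any |t(k)| above the 5% critical value among the cuts considered. Results at n = 100, from 20,000 replicates:

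| How the cut is set | False-positive rate |
|---|---|
| Fixed median, or from the thickness distribution alone | about 5% |
| Median and tertiles tried against the tested outcome | about 11% |
| Five quantiles tried (25, 33, 50, 67, 75%) | about 16% |
| Every cut in the middle 50% of patients | at most about 26–27% |
| Every cut in the middle 80% of patients | at most about 40–41% |

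**2. Cut searched against weaning, then function tested at that cut.** The rate depends on the assumed correlation between function and weaning.

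| Correlation | n = 100 | n = 40 |
|---|---|---|
| 0 | 5% | 5% |
| 0.3 | 7–8% | 7–8% |
| 0.5 | 11–13% | 10–12% |
| 0.7 | 16–21% | 15–20% |

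**3. Time to wean.** Here the variable already examined is the one compared. If a log-rank test were added (exponential times, 0% or 20% censoring, n = 100), the rate would be 5–6% at a fixed median, 12–13% with median and tertiles tried, and at most 28–44% with every cut searched. A score approximation without censoring gave 26% and 39% for the full search.

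**4. Power lost by splitting.** A median split of a normal variable multiplies the correlation by 0.798. Power ≈ Φ[ atanh(r) × √(n − 3) − 1.96 ]. For r = 0.3 and n = 100:

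- continuous: 0.3095 × 9.849 − 1.96 = 1.09, so 86%
- median split: r = 0.3 × 0.798 = 0.239; 0.244 × 9.849 − 1.96 = 0.44, so 67%

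Simulation (20,000 replicates) gave 87% against 68% at n = 100, 65% against 46% at n = 60, and 48% against 32% at n = 40.

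**5. Which change defines the groups.** This point is separate and conditional, because the plan does not say that nadir is used. Longer ventilation gives more scans and so a deeper minimum, even without any true link. The check used a pre-fixed median split on nadir change, time counted from baseline, a log-rank test and n = 100. Scans were daily or every 2 days, and mean ventilation was 7 or 10 days.

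- True between-patient SD large relative to scan noise (noise SD 2% with true SD 15–20%, or 5% with 20%): 6–15% false positives.
- Noise SD 5%, true SD 10%: 19–33%.
- No true change at all (the extreme case): 44–73%.
- 5-day change with time counted from day 5: 4–7% throughout.

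**The case against.** The wording on the cutoff can be read as referring only to the distribution of thickness change. On that reading there is no inflation. The dependence on earlier results governs whether the split is done, not where the cut falls, and nowhere does the plan describe searching cutoffs against an outcome. The 26–44% figures are therefore ceilings for conduct the plan does not state. For function, having seen weaning first costs little at low correlations: 5–8% at correlations of 0 to 0.3.

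The weaning objective does not rest on the split, because days to wean and total ventilator time are already analysed with thickness change kept continuous. The log-rank figures concern a test the plan never names. The list of continuous variables is open-ended and may cover MEP and CPF. Finally, the split is plainly secondary in a cohort study with a separate primary test.

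Most of this is fair, and it limits the size of the problem. It does not remove it. The harmless reading is possible, but the text does not commit to it. Being optional does not tell a reader how to interpret a result. Function is also an awkward fit in the open list, which holds independent variables with thickness change as the dependent variable. The text supports saying that function is not named there, and no more than that.

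**Conclusion.** The concern holds. The gap in the text is certain. How much inflation or power loss follows is not, because that depends on how the cutoff would be chosen and on what the open-ended list was meant to include.

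A cut set without sight of outcomes does no harm to the error rate. Trying a few conventional cuts against the tested outcome roughly doubles or triples it (11–16%), and the higher figures are upper bounds. If the regression was not meant to cover MEP and CPF, the first secondary objective gives up about 19 percentage points of power at n = 100 (87 − 68) and 16 at n = 40 (48 − 32), at an assumed correlation of 0.3. If it was, the better analysis already exists and only needs naming. The nadir result is a conditional warning about one way of forming the groups. The primary Wilcoxon comparison is untouched. This should be corrected, but it does not threaten the main result.

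**What to change.** 1. Name linear regression of MEP and of CPF on continuous percent change in expiratory muscle thickness as the planned analysis of the first secondary objective. State which change is used, for example baseline to the last scan before the function test.
2. If groups are kept, fix the rule now without reference to outcomes, for example a median split of the 5-day change, which the SAP already uses. Label any other cutoff exploratory.
3. If time to wean is compared between groups, name the test if one is intended. Do not define the groups by nadir change with time counted from baseline. A 5-day change with time counted from a day-5 landmark avoids that problem.

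Items 1 and 2 change SAP wording only. They need no new data and give up only the freedom to choose a cutoff later. The landmark in item 3 has a real cost, and only if that comparison is kept: it leaves out patients whose ventilation ends before day 5, which is 25–39 of 100 under assumed durations, with deaths not modelled. By Schoenfeld's formula with equal groups, power = Φ[ ln(HR) × √d / 2 − 1.96 ], where d is the number weaned. At an assumed hazard ratio of 1.75, with all patients weaned:

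- d = 100: 0.560 × 5.00 − 1.96 = 0.84, so 80%
- d = 75: 0.560 × 4.33 − 1.96 = 0.46, so 68%
- d = 61: 0.560 × 3.91 − 1.96 = 0.23, so 59%

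The landmark is a trade-off for the sponsor to weigh. Items 1 and 2 do not depend on it.

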Primary objective: to establish the effects of critical illness and mechanical ventilation on thickness of the abdominal expiratory muscles.

Secondary objectives:

- to establish the effect of changes in abdominal expiratory muscle thickness on the expiratory muscle function.

	
 - to establish the correlation between changes in thickness of the abdominal expiratory and inspiratory muscles. - to study whether changes in the thickness of the abdominal expiratory muscles also affects weaning outcome, and ICU readmission due to respiratory complications.
Study design	Prospective cohort study.
Study population	Patients who have been mechanically ventilated at the intensive care unit (ICU)
Inclusive criteria	
 - Age > 18 years - Invasive mechanical ventilation < 48 hours - Expected duration of mechanical ventilation > 72 hours
Exclusive criteria	
 - Past medical history of neuromuscular disorders - Mechanical ventilation > 48 hours within the current hospital admission - BMI > 35 kg/m² - Pregnant women - Open abdominal wounds at proposed location of the ultrasound probe, due to recent abdominal surgery
Sample size	100 subjects
Recruiting subjects	
Because mechanical ventilation is a requirement for eligibility, the participants frequently will be incapable of consent at the time of inclusion. Therefore, we will ask delayed informed consent from the patient as soon as he/she is capable of providing consent.
 
If patients are not able to give consent during their hospital stay, we will send an opt-out letter to the patient.

Intervention	Data from ultrasound measurements and from the electronic patient record will be obtained / analyzed. One additional blood sample will be obtained within 24 hours after inclusion, during planned blood collection (from arterial line or venous puncture).
Study endpoint	- Thickness of the abdominal expiratory muscles (external oblique, internal oblique, transverse abdominis muscle), during the inspiratory and expiratory phases of breathing.

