Study parameters	
 - Thickness of the diaphragm muscle - Inflammatory markers (TNF-alpha, IL-6, IL-10) at inclusion (measured from blood sample using ELISA technique). - Respiratory function parameters: maximum inspiratory pressure (MIP), maximum expiratory pressure (MEP), cough peak flow (CPF), diaphragm pressure and diaphragm electrical activity (in selected patients with these measurements available in clinical practice). - Mechanical ventilation parameters. - Weaning outcome - Ventilator associated pneumonia (VAP) - Follow-up of 6 weeks: readmission to ICU / hospital, reason for readmission, pneumonia acquired after discharge when subject is hospitalized. - Critical illness parameters (e.g. medication, APACHE II score) - Patient characteristics (e.g. gender, age, neurological and cardiopulmonary co-morbidities, BMI) 
This data will be retrieved from the electronic patient record and anonymously filed in a database.
 
Data on muscle thickness (thickness of diaphragm muscle and expiratory muscles) will be collected directly

	from ultrasound measurements on the ultrasound device.

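### The optional function analysis removes between-patient size differences from the thickness measure but not from MEP or cough peak flow, so it can miss a real link; a baseline-adjusted regression is a cheap improvement

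*Combined protocol and SAP*

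**What the plan says.** - **Objective, secondary objectives:** the study aims "to establish the effect of changes in abdominal expiratory muscle thickness on the expiratory muscle function".
- **Statistical Analysis Plan, primary endpoint:** "Change in thickness will be presented as ratio change compared to baseline, to account for inter-subject variation in baseline thickness".
- **Statistical Analysis Plan, Subgroup analysis:** a comparison of high- and low-change subjects may be done, with a cutoff chosen once the data are seen. Within it, "Variables as respiratory function measurements can be compared between groups with a Student's t-test, using group average values". No covariate is named.
- **Study parameters:** the function measures are listed as "Respiratory function parameters: maximum inspiratory pressure (MIP), maximum expiratory pressure (MEP), cough peak flow (CPF), diaphragm pressure and diaphragm electrical activity", followed by a bracket, "in selected patients with these measurements available in clinical practice". The inflammatory markers are fixed at inclusion; the function measures have no time point. On source: "This data will be retrieved from the electronic patient record and anonymously filed in a database".
- **Intervention:** "Data from ultrasound measurements and from the electronic patient record will be obtained / analyzed". The only other study procedure is one blood sample, so the study schedules no strength or cough test of its own.

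**The concern.** The plan sees that patients start with muscles of different thickness and divides that difference out of the thickness variable. It does nothing comparable for function. A patient with thick muscles who has lost a fifth of them may still produce a higher MEP than a patient with thin muscles who has lost nothing. In an unadjusted comparison of two groups, that starting difference acts as noise in the outcome.

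Timing is also open. Elsewhere the plan measures thickness change at nadir, over the first 5 days, or from baseline to the last scan. The Subgroup analysis does not say which of these forms the groups, or how far from the scan a function value may lie.

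The function values come from the patient record, so the number of patients who have them, and how they differ from the rest, is unknown.

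A null result could be read as showing that thinning does not matter for strength or cough, which is the clinical argument of the Rationale. A positive result could be read as applying to the whole cohort when it describes only the patients tested.

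**Working it through.** **Inputs.** From the documents: 100 subjects, thickness as a ratio to baseline, and an unadjusted t-test for function. The sample size comes with no alpha, power, effect or SD, so there is no stated figure to reproduce. Everything else below is an assumption, shown as a range.

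**Step 1: how strongly can ratio change track function?** Let B be baseline thickness with coefficient of variation c, and R the ratio to baseline with mean m = 0.90 and SD s, independent of B. Let function be exactly proportional to current thickness B×R, with no measurement error. Then

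corr(R, B×R) = s / √[s² + c²(m² + s²)].

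Example with c = 0.30, s = 0.15: 0.15 / √[0.0225 + 0.09 × (0.81 + 0.0225)] = 0.15 / √0.0974 = 0.15 / 0.312 = 0.48.

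| CV of baseline thickness | s = 10% | s = 15% | s = 20% |
|---|---|---|---|
| 20% | 0.48 | 0.63 | 0.74 |
| 30% | 0.34 | 0.48 | 0.59 |
| 40% | 0.27 | 0.38 | 0.48 |

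The table comes from a simulation of 400,000 patients; the formula agrees within 0.01 in every cell. Squared, the extremes are 0.27² = 7% and 0.74² = 55% of the variance in function.

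**Step 2: what can the t-test detect?** With two equal groups, two-sided 5% and 80% power, the detectable standardised difference is d = (1.96 + 0.84) × √(4/N):

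- N = 100: 2.80 × 0.200 = 0.56
- N = 50: 2.80 × 0.283 = 0.79
- N = 30: 2.80 × 0.365 = 1.02

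N here is the number of patients with function data, which the plan does not give.

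**Step 3: power for a true proportional link.** Same model, median split, with 20% residual variation in function unrelated to thickness, CV 30–40% and ratio SD 10–15%:

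| Patients tested | Planned t-test | Regression on ratio change and baseline thickness |
|---|---|---|
| 100 | 48–92% | about 100% |
| 50 | 27–68% | 92–100% |
| 30 | 17–44% | 72–96% |

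Part of the gain comes from not splitting the ratio into two groups. Continuous ratio change without baseline thickness reaches 40–86% with 50 tested, so the adjustment adds more on top.

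**Step 4: sensitivity to noisier function tests.** With 50 tested, CV 30% and ratio SD 10–15%, power rises from 37–66% to 93–100% at 20% residual variation, and from 25–41% to 40–73% at 40%. A fresh run agreed within a few percentage points. The gain shrinks as function becomes noisier but does not disappear.

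**The case against.** **The plan does not say that raw values will be used.** A reader might infer that it commits to absolute MEP and cough flow. It does not: percent-predicted or adjusted values are not excluded. This stands, and it is why the point is conditional on function being analysed as recorded. What the text does establish is that no scale, baseline, covariate or time point is given.

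**A correlation below 1 is not a missed link.** This also stands. With no measurement error and all 100 patients tested, the median-split t-test has power of 81%, 98% and about 100% at CV 30% (ratio SD 10%, 15%, 20%), and 99% or more at CV 20%. At CV 40% it has 57%, 89% and 98%. With 50 tested at CV 30% it has 52%, 82% and 96%. A reader might infer that the test will fail, or that ratio change can explain only a small part of function. At CV 20% it explains up to 55%, so neither inference is supported.

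**Who is tested is not documented.** A reader might suppose that only awake patients or survivors contribute, or that sedation prevents testing at inclusion. The documents say none of this. The bracket about selected patients may cover only diaphragm pressure and electrical activity. What is documented is retrieval from the record and the absence of a study-scheduled test. Selection is possible, but its direction and size are unknown.

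**Another route may exist.** The Statistical Analysis Plan's list of continuous variables for linear regression is open-ended and could take MEP or cough flow. It names neither and does not bring in baseline thickness, so it helps only in part.

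**The stakes are limited.** The comparison is optional, serves one secondary objective and leaves the primary endpoint untouched. This stands and sets the severity.

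**Conclusion.** The concern holds in a limited form. The plan takes between-patient variation out of the thickness variable, "to account for inter-subject variation in baseline thickness", and specifies nothing that would take it out of function. If function is analysed as recorded, the planned test can miss a real link, mainly with wide variation in baseline thickness, small changes, or only some of the 100 patients tested. With high variation and few tested the loss of power is large; with low variation and nearly everyone tested it is negligible.

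These sizes rest on assumed proportionality, a 10% mean loss, and assumed CVs, SDs and residual variation. The documents give none of them, nor the number tested.

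This is more than missing detail, because a better analysis of data the study already collects had higher power in the noisier settings of Steps 3 and 4. It is a cheap improvement of low severity.

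**What to change.** Replace the high/low t-test for function with two linear regressions, one for MEP and one for cough peak flow:

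- Explanatory variable: continuous ratio change, taken from the scan closest in time to the function test.
- Covariates: baseline thickness, sex and age.
- State the scale on which function is analysed.
- Report how many patients have each test, and how they differ at baseline (for example age, sex, APACHE II) from those without it.
- State the result as an association in tested patients.

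Regressing function on absolute thickness alone is not a substitute. It would show a positive relation even if nobody's muscles changed, because larger muscles are stronger, and the objective concerns change. Its perfect correlation under the model above only restates the assumption that function is proportional to current thickness.

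The cost is some SAP wording and a little analysis of data already collected, with no new tests for patients. The small downside is a narrower stated conclusion for this objective.

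### The optional Kaplan-Meier comparison of time to wean fixes neither the thickness-change measure, its direction and window, nor the start of the clock, which leaves room for immortal-time bias

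*Combined protocol and SAP*

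**What the plan says.** All references are to the Statistical Analysis Plan in the combined document.

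- **Subgroup analysis.** The analysis is optional: "a subgroup analysis may be performed to compare the subjects with high change in expiratory muscle thickness" with those with low change. On the split: "A cutoff value to divide these groups will be determined based on how data will emerge". On the outcome: "a Kaplan-Meier survival analysis will be carried out to quantify differences in time to wean between groups". No change measure, direction, measurement window or time zero is given, and no test is named.
- **Primary endpoint.** Change is taken over the period of ventilation as a ratio to baseline: "The Wilcoxon signed-rank test will be used to compare changes in baseline and nadir values". The association analyses also use nadir change.
- **Same section, time variables.** The list of continuous variables runs "duration of mechanical ventilation, days taken to wean, inflammation at inclusion", so ventilation time and weaning time are separate quantities. Neither has a stated starting point.
- **Same section, early change.** A regression relates "change in thickness during the acute stage of MV (5 days) with the total time spent on the ventilator".
- **Correlation between diaphragm and expiratory muscles.** This part uses "change in thickness between baseline and the last data point obtained", and then the slope of a fitted curve.

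The plan therefore contains four measures of change (nadir, 5-day, last scan, slope) and assigns none of them to the Kaplan-Meier comparison. It mentions no landmark or time-dependent method.

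**The concern.** A group used in a survival comparison should be defined by information available when the clock starts. If it is defined by something observed while the clock runs, time on study helps to decide the group. A patient has to stay ventilated long enough to record a deep nadir, and that waiting time is then credited to the high-change group. This is immortal-time bias.

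Whether thickness change affects weaning outcome is a stated secondary objective, and this is the planned group comparison of time to wean. A spurious separation could be read as evidence that muscle change delays weaning.

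**Working it through.** **1. Mechanism.** Take a patient with no true change. Given the baseline reading, let p be the chance that one later scan falls below the high-change cutoff through reading error alone. With k independent scans, P(nadir below cutoff) = 1 − (1 − p)^k, which rises with k. If scans continue through ventilation, k rises with ventilation time. If ventilation time is also the outcome, the groups differ in outcome by construction.

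**2. Inputs.** The documents give n = 100 (Sample size, stated without a derivation, so there is no calculation to reproduce) and expected ventilation above 72 h (Inclusive criteria). The rest is assumed:

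- lognormal ventilation time, median 7 days, sigma 0.6–0.8;
- reading error 5% on baseline and every scan; daily scans;
- drift 0, or −1 or +1% per day with SD 1% per day between patients;
- median split, all patients wean, log-rank test at two-sided 5%;
- weaning unrelated to thickness, so a sound analysis rejects in about 5% of trials.

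**3. Nadir grouping, clock = total ventilation time.**

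| Thickness course | Log-rank rejection |
|---|---|
| No drift, no minimum ventilation time | about 59–78% (median gap about 2.0 to 3.4 days) |
| No drift, 3-day minimum | about 25–44% |
| 1%/day loss | about 72–99% |
| 1%/day thickening | about 10–19% |

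Expected duration is not actual duration, so both no-drift rows are plausible. The way the minimum is imposed also matters: one variant gave 63% at sigma 0.8. A different model, with at least 3 days before weaning starts and median ventilation of about 7.6 or 10.2 days, gave 22–45% with no drift (gap 0.8 to 2.3 days) and 84–98% with loss. Widening the first model to medians of 5.5–10 days, sigma 0.4–0.8 and error 3–8%, without a minimum, gives 26–84% with no drift, 67–99% with loss and 6–40% with thickening.

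**4. Last-scan grouping, total time.** If high change means greater loss, rejection is about 5–6% with no drift. It is 73–88% under loss (high-change group appears to wean later) and 71–85% under thickening (appears to wean earlier). If high change means absolute change, the thickening result reverses to later (+2.5 days, 88% at sigma 0.6). With mean drift 0 but SD 1%/day between patients, absolute change gives +1.9 days and 66%. Direction therefore depends on a definition that the plan does not give.

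**5. Where the bias shrinks.**

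- Clock is the weaning phase and scans end when weaning starts: 5–6%. If scans continue into weaning, nadir gives 20–23% (no drift), 50–54% (loss) and 8–9% (thickening).
- Change limited to the first 5 days, clock not moved: 4.5–6.7% in the model with at least 3 days before weaning, and 5% (no drift) or 9% (loss) in the lognormal model with a 3-day minimum. Without a minimum it is 9–15%, 15–25% and 5–9% for no drift, loss and thickening.

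**6. Day-5 landmark.** Rejection is 3–8% in all 156 settings run (mean 5.6%).

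**7. Cost of the landmark.** P(ventilated under 5 days) = Φ(ln(5/median)/sigma).

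- Smallest: median 10, sigma 0.4: Φ(−1.73) = 0.04.
- Median 7, sigma 0.6: Φ(−0.56) = 0.29.
- Largest: median 5.5, sigma 0.8: Φ(−0.12) = 0.45.

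Detectable hazard ratio with 80% power = exp(2 × 2.8016/√events), for equal groups with all patients weaning: 1.75 for 100 patients, 1.94 for 71 and 2.13 for 55.

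**The case against.** The strongest reply is that the plan commits to none of the three conditions. That is correct. A reader might infer that the SAP as written contains immortal-time bias, or that its result will be spurious. The documents do not support that: the measure, the scan schedule and the clock are all open, and the separate listing of weaning days allows a clock that runs only over the weaning phase.

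The case for nadir is also not decisive. Where the SAP says that "nadir change in expiratory muscle thickness will be assessed using a linear regression model", thickness change is the dependent variable and ventilation time the independent one, the reverse of the Kaplan-Meier question. The text just before the subgroup section uses last scan and slope. Slope grouping is much less exposed where patients differ in drift (5–9% rejection with drift SD 1%/day), though it gave 17–23% with no drift at all. Still, nadir is the measure of the primary analysis, and the subgroup analysis is to follow from the earlier results, so an analyst could use nadir without departing from the text. Avoiding nadir is not enough either, because last-scan change is biased when thickness drifts on average.

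A reader might also infer that the bias always makes the high-change group appear to wean later. Step 4 shows that this fails for last-scan change.

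Finally, the analysis is optional, and the SAP separately relates 5-day change to ventilator time. Both points stand and lower the priority. The 5-day regression does not repair the group comparison, but it supplies a suitable window.

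**Conclusion.** The point holds in conditional form. The comparison is under-specified in a way that permits a biased analysis. Under nadir grouping, continued scanning and a total-time clock, the mechanism is certain but its size is not: with no true effect and no drift, rejection of roughly 25–78% depending mainly on the minimum ventilation time, more with loss of thickness, much less with thickening. These figures rest on assumed ventilation times, reading error, drift and test. They use a median split, so they do not include any further effect of choosing the cutoff from the data. The primary baseline-to-nadir comparison is not affected by this point. It is a cheap improvement of low priority.

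**What to change.** Keep the group comparison and rewrite it as a day-5 landmark:

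- state whether day 0 is intubation or inclusion, since inclusion may come up to 48 h into ventilation;
- include patients still ventilated at day 5;
- classify them by change from baseline to day 5, stating whether high means loss, thickening or absolute change, with a cutoff fixed in advance, such as the median;
- start the clock at day 5;
- state how death before weaning is handled in the analysis.

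If time to wean is meant as the weaning phase only, say so and classify by scans taken before weaning starts.

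The cost is SAP wording and the loss of patients weaned before day 5 (step 7), with a matching loss of precision. The result would apply only to patients ventilated beyond day 5.
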